### 6.1.3. Handling of Partial Dates

The following conventions will be used to impute missing portions of dates for adverse events and concomitant medications in determining whether the events occur during certain study period. Complete missing date will not be imputed.

#### Adverse events

##### A. Start Dates

- 1) If the year is unknown, then the date will not be imputed and will be assigned a missing value.
- 2) If both the month and day is unknown, then:
  - i) If the year matches the first dose date year, then set the month and day to the same as the first dose date.
  - ii) Otherwise, assign ‘1 January.’
- 3) If only the day is unknown, then:
  - i) If the month and year match the first dose date month and year, set the day to that of the first dose date.

ii) Otherwise, assign the first day of the month.

**B. Stop Dates**

- 1) If the year is unknown, then the date will not be imputed and will remain a missing date.
- 2) If the month is unknown, then assign ‘December.’
- 3) If the day is unknown, then assign the last day of the month.

**Prior/concomitant medications**

Partial start dates of the concomitant medications will be assumed to be the earliest possible date consistent with the partial date. Partial stop dates of prior and concomitant medications will be assumed to be the latest possible date consistent with the partial date. In the case of the completely missing stop date, medication will be assumed to be ongoing.

**6.1.4. Handling of Early Termination Visit Information**

In the event that a subject is terminated early from this study, the early termination visit data will be imputed. The imputation method depends on the reasons of missing, i.e. informative or non-informative missing. Please see more details about the reasons in Table 2 in Section 6.1.5.

For by visit summaries, the early termination visit data can be analyzed at the closest scheduled visit. If the closest visit has observed data, the early termination data will be assigned to the next available visit.

**6.1.5. Data Imputation Specifications**

For the safety analyses, no imputation of missing events or assessments are allowed.

For the primary efficacy endpoint (complete cure rate at Day 28), the algorithms listed below will be followed.

Any informative missing will be counted in as non-responders (failures) in the estimation of the treatment complete cure rates. Any non-informative missing will be imputed using Last Observation Carried Forward (LOCF) in the estimation of the treatment complete cure rates.

Table 2 Informative or Non-Informative Missing

Dropouts Due to			
Lack of Efficacy	Drug Related Adverse Event	Lost to Follow-up	All Other
Informative	Informative	Non-informative	Non-informative

For sensitivity analyses regarding the primary endpoint, the Observed Cases (OC), LOCF, and multiple imputation (MI) method will be used as appropriate approaches in addition to the imputation approach described for the primary efficacy analysis above. In addition, the Observed Case (OC) and LOCF methods will be used as sensitivity analyses for exploratory endpoints. Section 6.3 specifies in detail about imputation methods applicable to them.

The MI method assumes data are missing at random (MAR). The seed number is 626. The number of imputations is 5.

Step 1: Non-monotone missing data will be imputed using the fully conditional specification (FCS) method separately for each treatment arm since the response missingness could be due to treatment. A logistic regression will be used for binary data, and a discriminant function method will be used for ordinal data or classification variable with more than two levels if necessary. The following covariates will be included in the imputation model: treatment, clinical site (small sites pooled), baseline evidence of burrows and baseline score of lesions. In this step, MI procedure with FCS statement will be performed using SAS version 9.4.

Step 2: The combined imputed data sets will be analyzed using a Cochran-Mantel-Haenszel test and a logistic regression.

Step 3: The results from the analysis based on the multiply-imputed datasets will be combined by the MIANALYZE procedure in the SAS version 9.4. The p-value, estimate of odds ratio (Natroba™ vs Placebo), and the 95% confidence interval of odds ratio estimate from each multiply-imputed data set will be combined (Wilson & Hilferty, 1931; Gorja, 1992; Rubin, 1987; Li et al., 1991).

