**6.7 Early Termination Procedures**

The term "Early Termination" refers to a subject's non-completion of a study whether by his or her own choice or the investigator's decision or due to discontinuation of the study by ParaPRO LLC. In the absence of a medical contraindication or significant protocol violation, every effort will be made by the Investigator to keep the subject in the study. Should the subject decide to withdraw, an early termination visit should be conducted, which will include all procedures

normally done at Visit 3. The ET subject will not be dispensed 5% Permethrin and the PI will refer the subject to their primary care physician for follow-up.

The primary reason for a subject withdrawing prematurely should be selected from the following categories:

***Adverse Event or Serious Adverse Event***—events that are associated with discontinuation.

***Noncompliance with protocol***—the subject failed to adhere to the protocol requirements. The deviation necessitated premature termination from the study.

***Withdrawal of Consent***—subject desires to withdraw from further participation in the study in the absence of an adverse event or a medical need to withdraw.

***Lost to Follow-up***—the subject did not return for one or more follow-up visit(s) following dispensing of test drug. The reason was unknown and appropriate due diligence was exerted by the investigator to contact the subject and encourage their return.

***Other***—causes of premature termination from the study other than the above, such as theft or loss of IP, termination of study by ParaPRO LLC, etc. The details of the premature termination in this “other” category should be documented fully.

The investigator should notify Concentrics Research promptly when a subject is withdrawn, or if the study is stopped at his/her site by the IRB or if the investigator elects to stop the study.

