### **7.3 Prior Medications and Concomitant Medications**

Investigator's need to be aware that patients often have severe pruritus and will be prescribed medications as well as take OTC medications to treat this condition. The PI needs to inform the subject of prohibited topical medications used for itching or other indication, including over-the-counter (OTC) cortisone products, as these may interfere with efficacy evaluations. Non-medicated lotions are allowed after IP is washed off (e.g., non-scented, hypoallergenic, etc.). Subjects will be instructed not to take any oral prescription medications without prior consultation with the Investigator unless their primary physician otherwise instructs. Oral Benadryl® (diphenhydramine) and other oral OTC anti-pruritics are allowed for itch relief. Subjects will be instructed to tell their primary physician of their participation in this study if they consult their physician during the study. Any therapy taken by the subject in the 4 weeks before randomization (Visit 1) will be reported as prior medication. Any therapy started or

stopped by the subject during the study after randomization will be regarded as concomitant therapy.

All prior and concomitant medications including topical treatments (prescription and over the counter, vitamins, and mineral supplements, and/or herbs) will be documented and must include the following information:

- Medication name
- Indication
- Start date
- Stop date or “Ongoing”

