#### **7.4 Prohibited Medications**

Subjects should not use any scabicide within 4 weeks before Visit 1, or use any scabicide, or rescue Permethrin, prescription or OTC medicated lotions, other than the IP during the study, through Day 28. There will be no washout of prohibited medications, subjects will be excluded or withdrawn from the study for use of prohibited medications.

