## **4. EFFICACY PARAMETERS**

### **4.1. Scabies Assessment**

Skin will be examined on Days 1 and 28/ET to establish positive or negative evidence of active scabies infestation.

- Scabies diagnosis – active scabies infestation confirmed by clinical signs and symptoms (evidence of burrows or presence of scabies)

inflammatory/non-inflammatory lesions and pruritus) as well as by microscopic exam of skin scraping or dermatoscopy to demonstrate the presence of mites, eggs, and/or scybala. If dermatoscopy is used it should also confirm there are burrows on the skin.

- Primary Efficacy Endpoint – complete cure is defined as demonstration of clinical cure (all signs and symptoms have completely resolved, including burrows, inflammatory/non-inflammatory lesions and pruritus) and microscopic or dermatoscopic cure with demonstration of the absence of mites, eggs, and/or scybala, and dermatoscopy negative for burrows.

Lesions should be indicated on a body diagram and/or marked with skin marker; count of existing and new lesions will be recorded.

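### The SAP does not say whether an early-termination examination feeds the primary-endpoint LOCF, and the planned LOCF sensitivity run equals or nearly equals the primary analysis

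*SAP*

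**What the plan says.** SAP 4.1 fixes when the outcome can be observed: "Skin will be examined on Days 1 and 28/ET to establish positive or negative evidence of active scabies infestation". No efficacy examination is scheduled between those times. For a subject who withdraws, protocol 6.7 says "an early termination visit should be conducted, which will include all procedures" normally done at Visit 3, so an ET cure result can exist.

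Protocol 8.4 uses the observed Day 28 result where there is one, makes imputation depend on the reason for dropout, and leaves the detail to the SAP. SAP 6.1.5, Table 2, counts dropouts for lack of efficacy or a drug-related adverse event as failures. For lost to follow-up and all other reasons, "Any non-informative missing will be imputed using Last Observation Carried Forward (LOCF) in the estimation of the treatment complete cure rates".

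SAP 6.1.4 says "In the event that a subject is terminated early from this study, the early termination visit data will be imputed", with the method again depending on the reason. For by-visit summaries only, it then allows ET data to be placed at the closest scheduled visit, adding: "If the closest visit has observed data, the early termination data will be assigned to the next available visit".

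SAP 6.1.5 and 6.3.1 list observed cases (OC), LOCF and multiple imputation (MI) as missing-data sensitivity analyses for the primary endpoint. SAP 6.3.1 adds the index per-protocol (I-PP) and ITT populations.

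On prohibited treatment, protocol 7.4 says "subjects will be excluded or withdrawn from the study for use of prohibited medications". Protocol 7.3 restricts topical itch products, including over-the-counter cortisone, "as these may interfere with efficacy evaluations".

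**The concern.** LOCF needs a last observation, and here there are only two candidates. If it is Day 1, every non-informative dropout is a failure, since index subjects are infested at baseline, and the informative/non-informative split in Table 2 has no effect. If it is the ET examination, some dropouts count as cured. The primary cure rates depend on which is meant, and the SAP does not say.

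Three consequences follow.

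- The LOCF sensitivity run applies nearly the same rule as the primary, so one of the three missing-data runs tests almost nothing.
- If ET data are used, a subject withdrawn for taking another scabicide, classed under All Other and clear at ET, can count as completely cured. The stated objective is cure after a single treatment. No planned run scores such subjects as not cured.
- Table 2 cannot be filled from the withdrawal form alone. Protocol 6.7 says "The primary reason for a subject withdrawing prematurely should be selected from the following categories", but its list has no lack-of-efficacy entry and does not split adverse events by relatedness.

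**Working it through.** **Step 1. Reproduce the plan's figure.** Inputs from SAP 2.3.2 and protocol 8.1: 60% v 30% cure, two-sided alpha 0.05, Fisher exact test, 48 completers per group. Exact enumeration of two binomials gives power 0.8005, matching the stated 80.0%. Allowing for 20% dropout, 96/0.8 = 120. The sample size is not in dispute.

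**Step 2. Compare the primary rule with the LOCF run, column by column.**

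| Table 2 column | Primary | LOCF run, ET not used | LOCF run, ET used |
|---|---|---|---|
| Lack of efficacy | Not cured | Not cured | ET result, expected not cured |
| Drug-related AE | Not cured | Not cured | ET result; may be cured |
| Lost to follow-up | LOCF | Same as primary | Same as primary |
| All other | LOCF | Same as primary | Same as primary |

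With ET data unused, the two runs are identical. With ET data used, they differ in practice only for drug-related AE dropouts found cured at ET. The expected number per arm is 12 × (share of dropouts that are drug-related AEs) × (share examined) × (cure rate). If a quarter of dropouts are such cases and all are examined, this is 12 × 0.25 × 1 × 0.6 = 1.8 on Natroba and 12 × 0.25 × 1 × 0.3 = 0.9 on placebo. If half are, it is 3.6 and 1.8. The shares are assumptions; the documents give none.

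Protocol 6.7 defines lost to follow-up as not returning, so these subjects will normally have no ET examination and LOCF gives not cured. The open choice therefore falls mainly on the All Other column.

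**Step 3. Effect of the open choice on the primary.** Let d be the dropout fraction and e the share of dropouts examined at ET, with those examined clear at completer rates (generous, because ET precedes Day 28). All dropouts are assumed to follow the LOCF route.

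- Natroba rate = 0.60(1 − d) + 0.60·d·e
- Placebo rate = 0.30(1 − d) + 0.30·d·e

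The test is the single-stratum CMH with a and b cured of n and m, S = a + b and N = n + m: chi-square = (a − nS/N)² / [nmS(N − S)/(N²(N − 1))]. Power is by exact enumeration at 60 per arm.

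| d | e | Natroba v placebo | Power |
|---|---|---|---|
| 20% | 0 (ET unused) | 48% v 24% | 78.7% |
| 20% | 0.25 | 51% v 25.5% | 82.8% |
| 20% | 0.5 | 54% v 27% | 86.5% |
| 20% | 1 (ceiling) | 60% v 30% | 92.4% |
| 10% | 0 (ET unused) | 54% v 27% | 86.5% |
| 10% | 0.5 | 57% v 28.5% | 89.8% |

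Between ET unused and half used, the gap is about 8 points at 20% dropout and about 3 points at 10%.

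**Step 4. Withdrawn scabicide users clear at ET.** The documents give no uptake, so 1, 2 or 3 users per 60 are assumed, counted as cured.

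| Users in | Starting rates | Power with 1, 2, 3 users |
|---|---|---|
| Placebo only | 48% v 24% (no other dropout clear at ET) | 72%, 65%, 57% |
| Placebo only | 54% v 27% (half of dropouts clear at completer rates) | 82%, 76%, 70% |
| Natroba only | 48% v 24% | 84%, 88%, 91% |
| Both arms equally | 48% v 24% | 78%, 78%, 77% |

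The effect can go either way, and equal uptake costs little.

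**Step 5. What the other runs do with scabicide users.** Users who stay to Day 28 are scored as observed under protocol 8.4, and OC and MI keep that result. For withdrawn users, OC omits and MI imputes the Day 28 outcome. I-PP removes both groups (SAP 5.4).

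**The case against.** The documents lean towards one reading. The schedule gives Day 28 and ET one shared column, and the ET visit repeats the Visit 3 procedures. On the ordinary meaning of LOCF, that examination is the last observation. The by-visit rule is permissive and confined to summaries, so it does not contradict this. All of that stands: the two readings are not equally likely. But no text states it for the primary endpoint, and the sentence that ET data will be imputed points the other way on its face.

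A reader might infer more than the documents support:

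- *That the test is invalid or favours Natroba.* With equal true cure rates and equal dropout, the rejection rate is 4.7% at 24% v 24% and 4.8% at 30% v 30%. In that case the ambiguity affects power, not Type I error.
- *That 12 dropouts per arm is the planned case.* 20% is the stated maximum. The 92% figure also needs every dropout to be examined, which cannot happen if any are lost to follow-up.
- *That the choice could be made with treatment codes known.* The SAP is to be final before unblinding, and data stay blinded until lock.
- *That dropout is untested.* OC, MI and I-PP all differ from the primary.
- *That scabicide users necessarily score as cured.* One who sought other treatment while still infested might be classed as lack of efficacy, hence a failure. Scoring completers as observed is a legitimate treatment-policy choice.

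It is also fair that clarifying wording would resolve the ambiguity. It would not make the LOCF run informative.

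**Conclusion.** The point holds in limited form and should be fixed before unblinding. Two parts rest on the text alone: the SAP does not say whether an ET examination is the last observation for complete cure, and the LOCF sensitivity run equals the primary or differs only for informative dropouts cured at ET. Those will be few unless drug-related AE dropouts are common.

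The size rests on assumptions about ET attendance and ET cure: 79% v 87% power at the maximum dropout, and 87% v 90% at half that. The direction and size of any bias from other scabicides are unknown. Of the analyses that do differ from the primary, MI assumes missing at random and I-PP removes subjects, so no planned run shows how unfavourable the dropouts' outcomes would have to be to overturn the result.

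**What to change.** 1. Replace the LOCF sensitivity run for the primary endpoint with a tipping-point analysis over index dropouts. Keep OC, MI and I-PP.
2. Before unblinding and with FDA agreement, state one primary rule: an index subject who ends the study early with no Visit 3 (Day 28) assessment is counted as not cured, whatever the reason or ET result. Completers seen outside the window keep their observed Visit 3 result. Bring SAP 6.1.4 and 6.1.5 and protocol 8.4 into line. Reconcile the visit window, which is 28 ± 2 days in the schedule and Day 28 + 2 days in protocol 6.6. If Table 2 is kept instead, say whether the ET examination is the last observation and map each protocol 6.7 reason to a column.
3. Add one I-ITT sensitivity run that scores recorded use of another scabicide before Day 28 as not cured, from the concomitant medication data already collected (SAP 3.4).

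Cost: wording in the sections above and SAP 6.3.1, a short tipping-point program and one extra CMH run, with no new data. Protocol 8.5 and SAP 1 require FDA agreement before the primary analysis is altered. I-ITT power at the maximum 20% dropout should then be quoted at 48% v 24%: about 79% by CMH, or 73% by Fisher. The like-for-like figures in 48 completers per group are 85% and 80%. Counting dropouts as not cured does not remove bias from unequal dropout; the tipping-point analysis addresses that.

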## **6.3. Efficacy Analysis**

### **6.3.1. Primary Efficacy Analysis**

The primary efficacy endpoint is the proportion of index subjects completely cured of scabies by Day 28. Complete cure is defined as demonstration of clinical cure (all signs

and symptoms have completely resolved, including burrows, inflammatory/non-inflammatory lesions and pruritus) and microscopic or dermatoscopic cure with demonstration of the absence of mites, eggs, and/or scybala, and dermatoscopy negative for burrows.

The primary analysis will be based on the data from the I-ITT population. The proportion of index subjects who exhibit complete cure (Yes or No) at Day 28 will be estimated by treatment group. Natroba™ will be compared versus placebo, and the difference with 2-sided 95% confidence interval (CI) will be provided. A Cochran-Mantel-Haenszel (CMH) general association test adjusted by study site (small sites pooled) stratification will be performed to test at an alpha level of 0.05 for equivalence in the complete cure rates between the two treatment groups.

Sensitivity analyses will be performed on the primary efficacy endpoint to evaluate the robustness of the results using different methods of analysis and other populations.

The similar CMH test will be performed based on observed cases (OC) data, LOCF, and imputed data from MI method as sensitivity analyses.

A logistic regression analysis will be used assessing the treatment group difference in complete cure rate by Day 28. The model will include clinical site (or region?) and treatment group as factors, and possibly additional baseline characteristics or a covariate, only if appropriate. The odds ratio, 95% CIs and p-value for the comparison will be provided. For logistic regression modelling, the data imputation approach specified in Section 6.1.5 for primary analysis will be applied for missing values at Day 28.

The similar logistic regression will also be performed based on observed cases (OC) data, LOCF and imputed data from MI method as sensitivity analyses.

The complete cure rates at Day 28 will be summarized descriptively by treatment groups and by sites before and after pooling the sites.

Other additional sensitivity analyses include repeating the above two statistical analyses on I-PP population and ITT population.

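### Five imputations leave avoidable random-seed noise in the multiple-imputation sensitivity analysis of complete cure; the primary analysis is unaffected

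*SAP*

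**What the plan says.** SAP section 6.1.5 describes MI for the Day 28 complete cure endpoint under a missing-at-random assumption. It sets the seed and the number of imputations in advance: "The seed number is 626" and "The number of imputations is 5". The imputation step reads "Non-monotone missing data will be imputed using the fully conditional specification (FCS) method separately for each treatment arm", with site, baseline burrows and baseline lesion score among the covariates. Each completed dataset is analysed by a Cochran-Mantel-Haenszel (CMH) test and a logistic regression. For pooling, the SAP states: "The results from the analysis based on the multiply-imputed datasets will be combined by the MIANALYZE procedure in the SAS version 9.4". The p-value, the odds ratio and its 95% interval are all to be combined. No reason is given for five, and no Monte Carlo error is to be reported.

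SAP section 6.3.1 gives MI its place: CMH and logistic analyses are repeated on observed cases, LOCF and "imputed data from MI method as sensitivity analyses". The primary rule in section 6.1.5 is different: "Any informative missing will be counted in as non-responders (failures) in the estimation of the treatment complete cure rates", and non-informative missing values are filled by LOCF.

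Protocol section 8.1 and SAP section 2.3.2 plan 120 index subjects randomised 1:1, dropout of at most 20%, and cure rates of 60% and 30%.

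**The concern.** An MI result is itself a random draw: another seed on the same data gives another odds ratio, interval and p-value. The between-seed variance of the pooled estimate is the between-imputation variance divided by the number of imputations, so with five it can be noticeable when a fifth of a binary endpoint is missing.

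What is at stake is how precisely one planned robustness check is reported. A reader comparing the MI result with the primary, observed-case and LOCF results wants the differences to reflect the missing-data assumptions and not the seed. Fixing the seed makes the reported figure repeatable but leaves it one draw from the same spread.

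**Working it through.** **Inputs.** From the documents: 60 index subjects per arm, at most 20% dropout (12 per arm, leaving 48), cure rates 60% and 30%, two-sided 0.05, M = 5 imputations. Assumed: 20% missing in each arm, all of it imputed, and no site or baseline covariates in the imputation model.

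**The plan's own figures.** Exact enumeration of two-sided Fisher power gives 80.4% at 69 per group (55% versus 30%), 80.05% at 48 (60% versus 30%) and 80.6% at 37 (65% versus 30%). The SAP states 80.4%, 80.0% and 80.6%. Then 48 / 0.8 = 60 per arm, 120 in all. The design reproduces.

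**Simulation.** Within each arm a cure rate was drawn from Beta(x + 0.5, n − x + 0.5) and the missing outcomes from a binomial. The log odds ratio was pooled by Rubin's rules with a t reference. The 1-df chi-square, an unstratified stand-in for the CMH test, was pooled by the Wilson-Hilferty transform. Each fixed dataset was re-run with 20,000 seeds at each M shown.

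Design-like data, 29/48 versus 14/48 observed cures, 12 missing per arm:

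| M | Seed-to-seed SD of log OR | Central 95% of logistic p | Seeds with p < 0.05 |
|---|---|---|---|
| 5 | 0.085 | 0.0005 to 0.025 | 99.8% |
| 50 | 0.027 | 0.0015 to 0.0045 | about 100% |
| 100 | 0.019 | 0.0017 to 0.0038 | about 100% |

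The p-value range at M = 5 is 50-fold (0.025 / 0.0005). For the pooled chi-square the ranges are 0.0004 to 0.0149 at M = 5 and 0.0014 to 0.0029 at M = 100.

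**Closed-form check of the SD.** The formula is SD = √(B/M).
- Scaling the observed rates to 60 per arm gives 36.25 and 17.5 cures.
- The within-imputation variance is W = 1/36.25 + 1/23.75 + 1/17.5 + 1/42.5 = 0.150.
- The simulated missing-information fraction at large M is 0.196, so B = 0.150 × 0.196 / 0.804 = 0.0367.
- √(0.0367/5) = 0.086, √(0.0367/50) = 0.027 and √(0.0367/100) = 0.019, in line with the table.

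On the odds-ratio scale, the central 95% over seeds is 3.71 × exp(±1.96 × 0.085), or 3.14 to 4.38, at M = 5. At M = 100 it is 3.71 × exp(±1.96 × 0.019), or 3.57 to 3.85.

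**Share of seeds with logistic p < 0.05 as the result nears the threshold:**

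| Observed cures (of 48 per arm) | M = 5 | M = 100 |
|---|---|---|
| 26 vs 14 | 93% | about 100% |
| 25 vs 14 | 82% | about 100% |
| 24 vs 14 | 59% | 98% |
| 23 vs 14 | 30% | 4% |

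At 24 versus 14, the central 95% of p is 0.013 to 0.130 at M = 5 and 0.030 to 0.050 at M = 100. Repeating this row gave 57% to 59% of seeds below 0.05 at M = 5 and 96% to 98% at M = 100.

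**Averaged over simulated trials** (3,000 per setting, 60 per arm, 60% versus 30%), two seeds disagree about p < 0.05 as follows:

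| Missing | M = 5 | M = 50 | M = 100 |
|---|---|---|---|
| 5% | 2.0% | 0.6% | 0.5% |
| 10% | 4.1% | 1.0% | 1.0% |
| 20% | 9.1% | 1.9% | 1.6% |

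At 20% missing and M = 5, disagreement is 13.0% for 50% versus 30% and 2.1% for 70% versus 30%.

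**The case against.** The strongest reply is that nothing decisive rests on this number. MI is one of three missing-data sensitivity approaches, the primary analysis uses failure and LOCF rules, and the SAP ties no conclusion to the MI p-value. That stands. A reader might infer that the trial's verdict depends on the seed; the documents do not support this. Even the MI call at 0.05 is stable for a result at the design effect and moves only near the threshold.

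Second, five imputations are valid. Rubin's rules already charge for a finite M: the pooled standard error is √(0.150 + 1.2 × 0.0367) = 0.441 at M = 5 and √(0.150 + 1.01 × 0.0367) = 0.433 at M = 100, about 2% wider. This also stands. The loss of efficiency is small; the issue is the spread of the single reported result.

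Third, seed 626 is fixed in advance, so nobody can choose a favourable seed afterwards. That protection is real and should stay, but it does not reduce Monte Carlo error.

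Fourth, 20% is the plan's upper limit. Subjects who withdraw should have an early termination visit with the Visit 3 procedures (protocol section 6.7), and the SAP does not say how MI treats those results, so less may be imputed. That is why the 5% to 20% range is shown.

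A reader might also infer that MI is the only planned check that keeps every randomised index subject without counting dropouts as failures. That goes too far. LOCF also keeps everyone and could carry forward an early termination assessment. It must fall back on the infested baseline only for subjects with no such visit, and the documents do not say how many there would be.

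**Conclusion.** The point holds as a minor one. At the planned maximum dropout, five imputations give the reported MI odds ratio, interval and p-value a seed-to-seed noise that 100 imputations would cut by a factor of about 4.5 (0.085 / 0.019). The p-value varies visibly whatever the result. The primary conclusion does not change.

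The figures rest on arm-specific imputation without the SAP's covariates, an unstratified chi-square in place of the CMH test, and equal missingness in both arms. At 5% or 10% missing the effect is much smaller.

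**What to change.** In SAP section 6.1.5, change the number of imputations from 5 to 100 (at least 50) and keep seed 626. Reporting the Monte Carlo error of the pooled log odds ratio beside the result would be a useful addition. The cost is one number in the SAP and trivial run time for about 120 binary outcomes. The SAP is to be finalised before unblinding, so the change belongs before then.
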